9.3.3.2 Analytical Approach

WHO OSCi score at Baseline and Days 4, 7, 14, 21 and 42 will be summarized as a categorical variable. A Cochran-Mantel Haenszel (CMH) test for ordinal data will be used to compare the groups with respect to the percentage of participants reporting each category in the scale at each visit. Histograms of WHO OSCi scores at Days 4, 7, 14, 21 and 42 will also be produced.

Shift tables showing the changes from Baseline at each of Days 4, 7, 14, 21 and 42 in WHO OSCi score will also be provided.

The proportion of participants remaining at or below their baseline WHO OSCi score will be reported at Days 4, 7, 10, 14, 21 and 42 together with the corresponding 95% exact confidence interval. These proportions and confidence intervals will also be displayed graphically.

The maximum WHO OSCi score reported by each participant during the study will also be summarized and compared between the treatment groups with a CMH test for ordinal data. Within each maximum score, the number of days spent at that score will also be summarized. A histogram of maximum WHO OSCi score will also be produced.

WHO OSCI scores at all study days will also be listed.

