9.3.2. Secondary Efficacy Estimands

All secondary endpoints defined in Section 3 will be considered on the ITT population.

Intercurrent events strategies will be dependent on whether the endpoint is one evaluating the Objective 1 (to evaluate the effect of EDP1815 on the development and severity of complications of COVID-19 infection) or Objective 2 (To evaluate the effect of EDP1815 on length of hospitalization and recovery in participants with COVID-19) as follows:

Table 7: Intercurrent Event Strategies for the Secondary Estimands

Intercurrent event	Strategy for endpoints relating to Objective 1	Strategy for endpoints relating to Objective 2
Treatment discontinuation before the end of the 11 day treatment period	Treatment policy Actual values will be used regardless of treatment discontinuation	
Death prior to time of endpoint evaluation	Composite Subjects who die will be given a worst-case value from time of death	Competing risk Deaths will be accounted as a competing risk
Discharge prior to time of endpoint evaluation	While on treatment ¹ Values up to the time of discharge will be used. Treatment policy ² Actual values will be used regardless of inpatient/outpatient status	Treatment policy Actual values will be used regardless of inpatient/outpatient status
Initiating other experimental treatment not considered standard of care before endpoint evaluation	While-on-treatment Values prior to starting experimental treatment will be used	

¹ This will be used for all endpoints which are not recorded after discharge (e.g. S/F ratio).

² This will be used for all endpoints which are recorded after discharge (e.g. those relating to the WHO OSCI scale).

Population level summary measure will be assigned as appropriate to the type of endpoint as follows:

Table 8: Population Level Summary Measures for the Secondary Estimands

Type of endpoint	Population level summary measures
Categorical endpoint	Summary statistics, p-value for treatment difference (CMH test)
Binary endpoint	Risk difference between EDP1815 and placebo
Continuous endpoint	Mean difference between EDP1815 and placebo
Number of days with an event	Summary statistics
Time to event	Hazard ratio for EDP1815 vs. placebo

Full details of the individual secondary efficacy estimands will be provided in the SAP.

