The difference in proportions between the treatment groups in the percentage of participants remaining at or below their baseline WHO OSCI score will be reported together with the corresponding 95% confidence interval at Days 4, 7, 10, 14, 21 and 42.

A CMH test for ordinal data will be used to compare the treatment groups with respect to the maximum WHO OSCI score recorded by each participant. Within each maximum score, the time in days spent at that score will also be summarised.

Overall survival will be analysed using a Cox proportional hazards (Cox-PH) model. The model will include parameters for treatment together with the additional baseline covariates which were identified during the blinded review of the overall survival model. Participants who are still alive at the end of the 42-day study period or who withdraw prematurely from the study for reasons other than death will be censored on the day of their study completion/withdrawal. The hazard ratio for treatment difference with corresponding 95% confidence interval will be presented.

If during the course of the study, a newly approved medication for COVID-19 becomes part of the standard of care treatment at the investigational site, a further sensitivity analysis will be performed. A time-dependent covariate for use of the new medication (yes, no) will be included in the model described above together with its interaction with treatment.

Intubation and mechanical ventilation free survival will be analysed in the same manner as described for overall survival above.

Number of days requiring oxygen therapy, number of days with pyrexia, maximum daily temperature, minimum and maximum SpO₂ values will be summarised only.

Time to discharge will be analyzed using the Fine and Gray subdistributional hazards model to allow for the competing risk of death (Fine 1999). The model will include parameters for treatment together with the additional baseline covariates which were identified during the blinded review of the time to discharge model.

Subjects who are not discharged and are still alive at the end of the 42-day study period or those who withdraw prematurely from the study without being discharged or dying will be censored on the day of study completion/withdrawal.

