7.2 Covariates and Subgroups

The following covariates will be considered as possible prognostic factors for inclusion in the analysis models described in [Section 7.2](#):

- Age ≥ 60 years (yes, no)
- Gender (male, female)
- Race (Non-Hispanic/Latino white, non-white or Hispanic/Latino)
- Baseline WHO OSCI score (4, 5)
- Time since onset of symptom at Baseline (days)
- Presence of obesity: BMI $\geq 30 \text{ kg/m}^2$ (yes, no)
- Current type 1 diabetes (yes, no)
- Current type 2 diabetes (yes, no)
- Current hypertension (yes, no)
- Other current chronic cardiovascular disease (yes, no)
- Current chronic respiratory disease (yes, no)
- Active cancer, excluding skin basal cell carcinoma or localized squamous cell carcinoma (yes, no)
- Smoking status (current smoker, not current smoker)
- Neutrophils $> 8.0 \times 10^3/\mu\text{L}$
- C-Reactive protein (CRP) $> 40 \text{ mg/dL}$

Other covariates may also be considered if emerging research into COVID-19 suggests other possible prognostic factors for outcome that can be determined from the data captured on the CRF.

Prior to database lock, the inferential primary analysis model described in [Section 9.2.2](#) will be examined on the blinded data in order to determine which baseline factors may have a prognostic effect on the efficacy endpoints. Covariates will be selected for inclusion in the model using forward stepwise selection procedure with a 5% level of significance applied for both the selection and deselection of variables from the model.

Where applicable, the baseline value of the endpoint will be automatically fitted first, regardless of significance before additional covariates are considered. A maximum of 3 covariates, in addition to the

baseline value where applicable, may be selected for each model in order to avoid over-parameterization and a reduction in the efficiency of treatment estimates.

If, during the study, a new treatment is approved for use in COVID-19 and becomes part of the standard of care for hospitalized participants at the study site(s), additional sensitivity analyses will be performed using covariates defined by use of this treatment.

- For ANCOVA analyses of trough S/F ratio
 - New SOC covariate: 'yes' if taken at any time before Day 14, 'no' otherwise
- For ANOVA analyses of S/F ratio at Day X
 - New SOC covariate: 'yes' if taken prior to Day X, 'no' otherwise
- For time-to-event analyses

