8.4 Concurrent Illnesses and Medical Conditions

All summaries of concurrent illnesses and medical conditions will be presented by treatment group and overall using the ITT population.

Concurrent illnesses and medical conditions will be classified as 'current' if the end date is on or after the date of first dose of study drug, or the condition has been marked as ongoing. Otherwise they will be classified as 'past'.

Targeted questions will be used to report the following known comorbidities for COVID-19 as part of the medical history CRF page:

- Type 1 diabetes
- Type 2 diabetes
- Hypertension
- Other chronic cardiovascular disease
- Chronic respiratory disease
- Ongoing diagnosis of cancer

In addition, other medical history and concurrent illnesses will be captured and coded using the v23.0 of the Medical Dictionary for Regulatory Activities (MedDRA®).

The number and percentage of participants reporting each relevant medical condition will be summarized together with the following potential risk factors for severe illness with COVID-19 which will be assessed from the demographic and baseline data:

- Age ≥ 60 years
- Male
- Non-white or Hispanic/Latino
- Obesity (BMI ≥ 30 kg/m²)
- Current smoker
- Baseline WHO OSCI score of 5
- Baseline neutrophils $> 8.0 \times 10^3/\mu\text{L}$
- Baseline CRP $> 40 \text{ mg/dL}$

In addition, the number and percentage of participants reporting 0, 1, 2, 3, 4, ≥ 5 potential risk factors will be summarized.

All medical history will be summarized, individually for past and current conditions. All medical history will be listed.

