9.1.1.2 Blinded Model Fitting

Prior to database lock the models to be used in the primary analysis will be examined on the blinded data in order to determine which baseline factors may have a prognostic effect and should be included in the models. The covariates defined in [Section 7.2](#) will be examined in a model of trough S/F ratio and selected as covariates for the relevant model at a 5% level of significance using forward stepwise selection.

Baseline S/F ratio will be the first fitted term in the model regardless of significance. A maximum of 3 further covariates may be included in the model in order to avoid over-parameterization and a reduction in the efficiency of the treatment estimates.

Distributional assumptions underlying the models used for analysis will be also be examined during the blinded review by obtaining a normal probability plot of the residuals and a plot of the residuals versus the

fitted values (i.e. checking the normality assumption and constant variance assumption of the model respectively) to gain confidence that the model assumptions are reasonable.

If the distributional assumptions underlying the model are found not to be reasonable, a log-transformation of the response variable will first be considered. In this event, the LS mean treatment ratio will be presented instead of the LS mean treatment difference. If this model is also found to violate the distributional assumptions, then further models including other transformations or nonparametric alternatives will be explored. An addendum to the SAP will be produced prior to database lock and unblinding detailing the methods to be used will be produced detailing the model strategy to be used in this event.

This approach to the inclusion of baseline covariates which may have a prognostic effect on response will also be used for the Cox proportional hazards and Fine and Gray models to be used for the secondary analyses.

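### The CMH tests of WHO OSCI name no stratum; stratifying by baseline OSCI (4, 5) is a cheap gain in precision, not the repair of an invalid test

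*SAP*

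**What the plan says.** **The tests.** SAP 9.3.3.2 sets the test of OSCI by day: "A Cochran-Mantel Haenszel (CMH) test for ordinal data will be used to compare the groups with respect to the percentage of participants reporting each" (that is, each level of the scale, at every visit). The maximum score is "compared between the treatment groups with a CMH test for ordinal data". Protocol 9.4.1.2 agrees: it compares the arms by the same test in "respect to the maximum WHO OSCI score recorded by each participant". Protocol Table 8 (section 9.3.2) makes the CMH p-value part of the summary measure for categorical endpoints. None of these places gives a stratification factor or a score type.

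**Baseline OSCI.** SAP 7.2 has the baseline score, with levels 4 and 5, in its list of possible prognostic covariates. SAP 8.4 includes "Baseline WHO OSCI score of 5" among potential risk factors for severe illness.

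**Adjustment elsewhere.** S/F on Days 4, 7, 10 and 14 is analysed by ANCOVA with baseline S/F always in the model (SAP 9.3.1.2). SAP 9.1.1.2 says that the covariate approach "will also be used for the Cox proportional hazards and Fine and Gray models to be used for the secondary analyses"; the CMH tests are not mentioned. SAP 5.2 describes a blocked 1:1 list, with no stratification by OSCI.

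**The concern.** A CMH test exists to compare groups within strata. With no stratum it reduces to a single-table comparison, so a later OSCI score is tested without its own recorded baseline. S/F, the other main measure of the same illness, gets that adjustment.

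The link to baseline is closest for maximum OSCI. A participant who starts at 5 has a maximum below 5 only if the score has already fallen by the first post-baseline record.

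One stated purpose of the pilot is to judge endpoints for relevance and sensitivity and to inform later sample sizes (protocol 9.1, SAP 6). If OSCI is tested less efficiently than S/F, it may look less sensitive than it is. The OSCI-by-day table also goes to the DMC unblinded at every meeting, and the maximum OSCI table is in the efficacy set for the 60-participant review (SAP Appendix 1).

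**Working it through.** **The plan's own figure.** The only precision figure is the confidence-interval half-width for trough S/F (SAP Table 8). For 60 participants and SD 100, t(0.975, 58) × 100 × √(4/60) = 2.0017 × 100 × 0.2582 = 51.7, as stated; the other cells also reproduce. No power or precision is given for OSCI, so the rest uses assumed inputs.

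**The test.** In stratum h, let D_h be the EDP1815 sum of scores minus its expectation, n1h × (mean score in h). Let V_h = n1h × n0h / (n_h − 1) × (score variance in h). The row-mean-score statistic is Q = (ΣD_h)² / ΣV_h, compared with 3.84. The unstratified test treats everyone as one stratum.

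**Why the share at 5 matters.** If a share p starts at 5 and the mean scores of the two strata differ by d, the pooled variance carries an extra p(1 − p)d². The factor p(1 − p) is 0.05 × 0.95 = 0.048 at 5%, 0.20 × 0.80 = 0.16 at 20% and 0.35 × 0.65 = 0.23 at 35%. With few participants at 5 there is little to remove.

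**Inputs not in the documents (assumed).** Share at baseline 5; odds ratio of baseline 5 against 4 for a worse score; treatment odds ratio; two-sided 5% level. The power runs draw baseline scores at random with 30 per arm.

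**OSCI by day**, N = 60, proportional odds, modified ridit scores, 3000 to 6000 simulated trials per row. The rows at treatment odds ratio 2 and 3.5 assume Day 14 placebo proportions at baseline 4 of .10, .25, .20, .08, .15, .10, .06, .03, .03 for scores 0 to 8. The rows at 2.5 use an assumed nine-level distribution; repeating those at 5% and 20% with the Day 14 proportions moves each gain by no more than about 2 points.

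| Treatment OR | Share at 5 | Baseline OR | Power, no stratum | Power, stratified | Gain (points) |
|---|---|---|---|---|---|
| 2 | 20% | 3 | 29.8% | 31.4% | 1.6 |
| 2.5 | 5% | 3 | 49.9% | 50.2% | 0.3 |
| 2.5 | 20% | 3 | 46.9% | 49.8% | 2.9 |
| 2.5 | 20% | 6 | 43.0% | 48.5% | 5.5 |
| 2.5 | 30% | 6 | 41.4% | 49.6% | 8.2 |
| 3.5 | 5% | 3 | 75.1% | 75.3% | 0.2 |
| 3.5 | 5% | 6 | 74.0% | 74.6% | 0.6 |
| 3.5 | 10% | 6 | 73.2% | 76.0% | 2.8 |

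At the most favourable corner considered (treatment OR 3.5, 35% at 5, baseline OR 6), one run of 2500 trials gave 67% to 77%. That is 10 points, at the edge of the 0 to 9 range within simulation error. With a baseline OR of 1, stratifying costs about 0 to 2 points. Gains under about 1 point cannot be told from zero with these run sizes.

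**Maximum OSCI**, N = 60, treatment OR 2.5, 8000 trials per row. Assumed placebo proportions for maxima 4 to 8 are 65/15/8/4/8% from baseline 4 and 0/60/15/8/17% from baseline 5.

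| Share at 5 | Modified ridit | Gain | Table scores | Gain |
|---|---|---|---|---|
| 5% | 30.1% to 32.6% | 2.5 | 28.2% to 28.8% | about 0.5 |
| 20% | 24.6% to 34.1% | 9.5 | 26.3% to 29.0% | 2.7 |
| 50% | 21.6% to 34.6% | 13.0 | 25.1% to 30.0% | 4.9 |

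The zero for a maximum of 4 from baseline 5 builds in the floor and so favours stratifying. Gains are larger at larger treatment effects (treatment OR 4, 20% at 5, modified ridit: 40.5% to 58.3%).

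**Validity.** With no treatment effect, both tests reject in about 4 to 6% of trials, for both endpoints.

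**The case against.** The case for leaving the plan alone has real force.

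- **The loss may be nil.** Protocol 5.2 excludes ICU patients and those on CPAP, non-invasive or mechanical ventilation at screening, and protocol 5.1 requires hospitalization within 36 hours. On the scale in protocol 8.1.2, a baseline 5 then comes mainly from high-flow oxygen. The share may be small, and at 5% the by-day gain is negligible. This stands. The SAP does, however, provide for both levels.
- **Prognostic value is left open.** SAP 7.2 says possible and SAP 8.4 says potential, with selection by blinded stepwise modelling. This stands, and it is why the small cost when baseline OSCI is not prognostic belongs in the account.
- **The analyses are descriptive, in an unpowered pilot** (SAP 6 and 9), and no pre-defined rule for the extension rests on these p-values (SAP 7.4.3). This limits the severity. It does not remove the point, because the p-value is still the protocol's summary measure.
- **Baseline OSCI enters nearby analyses:** the shift tables, the endpoint of staying at or below baseline, and candidate covariates in the time-to-event models. None of these is a baseline-adjusted test of the score by day or of the maximum.

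A reader might infer that chance imbalance in baseline 4 against 5 biases these comparisons. It does not: such imbalance is already in the null distribution of the unstratified test, and type I error is held. A reader might also infer a large, certain power loss. The documents give neither the share at 5 nor its prognostic strength, so they do not support that.

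**Conclusion.** The point holds as a matter of precision. The two CMH tests leave out a recorded two-level baseline value of the same scale, and nothing in the plan explains why S/F is treated differently.

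With 60 participants, a share at 5 of 5 to 35%, a baseline odds ratio of 3 to 6 and a treatment odds ratio of 2 to 3.5, stratifying changes by-day power by about 0 to 9 points. It costs about 0 to 2 points if baseline OSCI is not prognostic. For maximum OSCI the gain is about 0.5 to 13 points at a treatment odds ratio of 2.5, over shares of 5 to 50% and two score types. All these sizes rest on assumptions; only the direction, given a prognostic baseline, is secure. The severity is minor. The point does not require modified ridit scores, although the maximum OSCI results show that the score type matters enough to be fixed in advance.

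**What to change.** Before unblinding, specify in SAP 9.3.3.2 and protocol 9.4.1.2, for each study day and for maximum OSCI: *CMH row-mean-score test stratified by baseline WHO OSCI score (4, 5)*. State the score type in the same sentence.

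Add a fallback: if a baseline stratum has no participants in one arm, use the unstratified test. Otherwise that stratum contributes nothing and its participants drop out of the comparison. This is not remote. If 3 of 60 start at 5, the chance that all three fall in one arm of 30 is 2 × C(30,3)/C(60,3) = 2 × 4060/34220 = 24%. Check the condition separately for each test, because missing scores can empty a stratum on one day and not another.

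While editing, reconcile the days: protocol 9.4.1.2 includes Day 10 in the by-day CMH test and SAP 9.3.3.2 does not.

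The cost is one stratification variable in the program and no new data. The downside is a very small power loss if baseline OSCI is not prognostic or few start at 5.

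### The CMH tests of WHO OSCI name no stratum; stratifying by baseline OSCI (4, 5) is a low-cost improvement with a small to moderate, assumption-dependent gain in power

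*SAP*

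**What the plan says.** SAP 9.3.3.2 tests OSCI at Days 4, 7, 14, 21 and 42 (protocol 9.4.1.2 also lists Day 10). It says a CMH "test for ordinal data will be used to compare the groups" at each visit. Maximum OSCI is "compared between the treatment groups with a CMH test for ordinal data". Protocol 9.4.1.2 reads the same way: "A CMH test for ordinal data will be used to compare the treatment groups with respect to the maximum WHO OSCI score". None of these sentences gives a stratification factor or says which scores are assigned to the levels.

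Baseline OSCI is known for the analysis. SAP 7.2 includes it, at levels 4 and 5, in a list introduced with "The following covariates will be considered as possible prognostic factors for inclusion in the analysis models". SAP 8.4 tabulates "Baseline WHO OSCI score of 5" among potential risk factors for severe illness.

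Covariates are chosen on blinded data by forward stepwise selection at 5%, with at most three beyond the baseline value. They enter the S/F ratio ANCOVAs. SAP 9.1.1.2 adds that the approach "will also be used for the Cox proportional hazards and Fine and Gray models to be used for the secondary analyses". The CMH tests are not mentioned there. SAP 5.2 describes a 1:1 blocked list and states no stratification by OSCI.

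**The concern.** CMH is a method for stratified tables. With no stratum named, the plain working reading is one treatment-by-score table. The S/F ANCOVAs always carry their own baseline value, and the Cox and Fine-Gray models can take baseline OSCI if it is selected. The ordinal tests have no such route, although baseline OSCI is the starting point on the same scale. The link is likely to be closest for maximum OSCI, because a participant who starts at 5 will often have a post-baseline maximum of at least 5.

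If baseline score matters, an unstratified test leaves the difference between the two baseline groups in the error variance. It also makes no allowance for chance imbalance in a 60-participant trial. What is at stake is sensitivity. The pilot is meant to judge endpoints partly on that property. The OSCI outputs also go to the DMC, which recommends at the 60-participant review whether to recruit 40 more.

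**Working it through.** **The plan's own precision figure.** The documents give no power or sample-size figure for the OSCI tests. The only precision figures are the primary-endpoint half-widths in SAP Table 8. With half-width = t(0.975, N-2) × SD × √(4/N) and SD 100, N=60 gives 51.7 and N=100 gives 39.7. Both match the table. They say nothing about OSCI, so the size of this point has to be simulated.

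**Inputs from the documents.** N=60 (possibly 100), 1:1 allocation, a scale from 0 to 8, baseline 4 or 5.

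**Assumed inputs, because the documents give none.**
- Two-sided alpha of 0.05.
- Placebo probabilities for levels 0 to 8, at baseline 4: .20, .20, .20, .08, .16, .06, .04, .02, .04.
- Proportional odds for baseline 5 versus 4, with odds ratio 1, 2, 4 or 8.
- Share at score 5 from 5% to 50%.
- Treatment odds ratio 1 (for type I error), 2.5 or 3.5.

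**Test.** In stratum h, let T be the sum of scores in the EDP1815 arm, n1 and n0 the arm sizes, n = n1 + n0, and SS the sum of squared deviations of the scores from the stratum mean. Then E = n1 × stratum mean and V = n1·n0·SS / [n(n-1)]. The statistic is (Σ(T-E))² / ΣV on 1 degree of freedom. The unstratified version treats everyone as one stratum. Both were applied to the same 40,000 simulated trials per scenario.

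**Power (%) at N=60, treatment odds ratio 2.5, unstratified → stratified:**

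| Share at score 5 | Prognostic OR 1 | OR 2 | OR 4 | OR 8 |
|---|---|---|---|---|
| 10% | 45.9 → 45.3 | 46.2 → 46.0 | 44.0 → 45.4 | 41.8 → 45.9 |
| 20% | 45.9 → 45.3 | 45.6 → 45.7 | 43.0 → 45.9 | 38.6 → 46.1 |
| 30% | 45.7 → 45.0 | 45.7 → 46.2 | 43.3 → 46.9 | 37.8 → 46.7 |
| 50% | 46.0 → 45.3 | 46.2 → 47.0 | 43.2 → 47.4 | 37.3 → 47.9 |

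Over shares of 5% to 50% and treatment odds ratios 2.5 and 3.5, the change in power is:
- prognostic OR 1 to 2: -0.8 to +0.9 points;
- OR 4: +0.3 to +4.8 points;
- OR 8: +1.8 to +12.2 points. The largest gain is at a 50% share and treatment OR 3.5 (60.8 → 73.1, 12.2 before rounding).

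At N=100 with a 20% share and treatment OR 2.5, the results are 66.6 → 67.1 (OR 2), 63.5 → 67.3 (OR 4) and 59.2 → 68.3 (OR 8). Type I error was 4.7% to 5.2% for both tests throughout.

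The Monte Carlo standard error of one power figure is at most √(0.25/40,000) = 0.25 points. A separate run of 20,000 trials per scenario at N=60 gave the same pattern.

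**Chance imbalance.** Suppose K of 60 participants are at score 5, with 30 per arm. The number X in one arm is hypergeometric. The arms differ by at least 4/30 = 13 percentage points when |2X-K| ≥ 4. The probability is 33% for K=12 and 40% for K=18. Both values of K are assumptions.

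**The case against.** The strongest reply is that nothing planned is broken. The trial is a feasibility-sized pilot without a power calculation, and SAP section 9 calls all analyses descriptive. Type I error holds either way. Baseline OSCI is tabulated by arm, so an imbalance would be visible. It also enters the OSCI evaluation through the shift tables and the proportion whose score has not risen above baseline. Nor is adjustment universal elsewhere: the Wilcoxon fallback for the primary endpoint and the protocol's difference in proportions are unadjusted. All of this stands, and it limits the point to a minor one. It does not remove it, because shift tables adjust no comparison and no other text supplies the strata.

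A reader might infer three stronger things that the documents do not support:
- **That the SAP chose to ignore baseline OSCI.** It is silent. It does not say the test is unstratified.
- **That baseline OSCI is an established prognostic factor.** SAP 7.2 says possible and SAP 8.4 says potential. It is one of 15 listed candidates and may not be selected.
- **That a material power loss is certain.** The larger gains need a prognostic odds ratio of about 4 or more and a score-5 group that is not rare. The documents give neither. Exclusion criterion 4 removes participants on CPAP, non-invasive or mechanical ventilation at screening, so score 5 is reached essentially through high-flow oxygen and the stratum may be small. At a 10% share and prognostic OR 4 the gain is 1.4 points (44.0 → 45.4).

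**Conclusion.** The point holds as a low-cost improvement, not as an error of validity. The CMH tests name no stratum, the covariate selection does not reach them, and a suitable two-level factor is already collected. At N=60, stratifying by it costs at most about 1 point of power if baseline OSCI is not prognostic. It gains about 0 to 5 points at a prognostic odds ratio of 4 and about 2 to 12 at 8. These sizes rest on an assumed outcome distribution, proportional odds, and assumed shares and effects. Severity is minor. Confidence is moderate: the gap in the text is plain, but the size of the benefit in this trial cannot be fixed from the documents.

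**What to change.** In SAP 9.3.3.2, for each tested study day and for maximum OSCI, specify the row-mean-score CMH test stratified by baseline OSCI (4, 5) and state the score type (for example, the scale values themselves).

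Add a sparse-stratum rule, for example to run the test unstratified if the blinded review finds fewer than a prespecified number at score 5. This matters because a stratum with participants from only one arm has V = 0 and contributes nothing to the test. The blinded review can see the size of the stratum but not its split by arm.

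The cost is one stratification term in the existing code and a few sentences in the SAP before unblinding, with no new data.

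A common odds ratio with 95% CI from a proportional-odds model adjusted for baseline OSCI would give an effect size for planning, but it is optional. Protocol Table 8 asks only for summary statistics and the CMH p-value for categorical endpoints. The model would have to be fitted for each day and for the maximum, and it adds a proportional-odds assumption on a nine-level scale with 60 participants.
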